## 11.0 Specimen Collection and Banking

Not applicable

## 12.0 Data Management

**Statistical Analysis:** Primary analyses for this pilot feasibility study center on patient satisfaction, treatment fidelity and adherence, with a secondary focus on changes observed on fatigue and dyspnea scales (obtained from the SGRQ), PImax and PEmax change, physical activity (steps per day and active hours per day), physical activity engagement (PROMIS activity engagement scale), and sex based differences. Treatment satisfaction will be measured qualitatively through analysis of recorded post-intervention interviews. Training frequency will be automatically assessed by the Bluetooth enabled tracker, which will also be developed to measure pressure changes to evaluate treatment gains for PImax and PEmax. Pre- and post-intervention data will be analyzed for correlation between symptom severity and respiratory muscle strength (PImax and PEmax) along with mean steps per day. Post-Intervention data collection will include PEmax, PImax, PROMIS and SGRQ scales (see above) to compare to baseline measures. The sample will be characterized using descriptive statistics for all variables, as appropriate. T-tests or non-parametric Wilcoxon rank sum tests will be used to compare continuous demographic and baseline clinical variables and chi-square or Fisher's Exact Test will be used for categorical (e.g., survey responses). An overall indicator of acceptability/usability will also be a) adherence via a % of total EMA assessments completed. Comparisons between device use and reported affective states, stress levels, COPD symptoms over previous 1-2 days will also be examined. We will also gather information from the post-trial interviews via qualitative analyses on aspects of the SAM program that would benefit from refinement. Qualitative data will be presented as themes of domains relevant for refinement of SAM. Exploratory Quantitative Analyses: Nonparametric analyses will compare emergency department visits and hospitalizations with SAMS EMA question responses. Comparisons will be run on EMA ratings and training use.

**Sample Size:** The purpose of this pilot study is not to confirm or refute hypotheses about treatment effectiveness (with corresponding emphasis on establishment of sufficient power for hypothesis testing); rather, we seek to demonstrate feasibility of the intervention and to obtain estimates of variability for the secondary outcome measures. Therefore, sample size was determined for pragmatic reasons rather than power (Leon, Davis & Kraemer, 2011). For this pilot study, we will recruit approximately 30 patients with COPD and, basing our estimated attrition on previous investigations, we anticipate that approximately 25 of these patients will complete all study-related visits. For this project's secondary aims (continuous outcome measures of self-efficacy, fatigue, and dyspnea), we use an in intent-to-treat analyses and 95% confidence interval (CI) estimates of the within group change scores (pre- to post-treatment) with precisions ranging from  $\pm 0.20$  to  $\pm 0.78$ . These correspond to estimated standard deviations of change scores of these variables, ranging from 0.5 to 2.0.

**Data Management.** Data report forms (DRF) for all data collection will be developed by the PI and study team. The Research Electronic Data Capture (REDCap) system provided through MUSC CTSA will be used to enter questionnaire and measurement data. REDCap is a secure, web-based application designed exclusively to support data capture for research studies. Only authorized study personnel will have access to the data tracking system. Data management including data quality assessment

(completeness and accuracy) will be done by the PI. Screening and post study questionnaires will be completed using a tablet based presentation or directly with the participant in paper format if so desired. Questionnaires will be entered into a HIPAA compliant and secure data management and storage. Key Informant Interviews will be recorded and transcribed. Transcription will only include the study ID number without PHI. EMA data, video capture, and training data submissions will be stored in a standard file format in RedCap and immediately erased from any portable storage device. Research staff will conduct daily checks of data transfer. A linkage file for the study ID number and PHI will be maintained in a password-protected server behind the MUSC firewall in order to link the questionnaire data, video, interview data, and EMA data. At the end of study, all patient video recordings will be deleted and erased from the research record.

Participants' data will not be stored on the cell phone but will be encrypted and sent to password protected server storage before being deleted from the phone. No PHI data are stored on the Bluetooth device therefore if lost no risk exists. Data will be collected and maintained on TACHL's secure research drive maintained by the Medical University of South Carolina. Databases are on password protected secure servers located behind the MUSC firewall. Access to these files will be limited to authorized members of the research team. Other authorized persons, such as regulatory authorities, may also have access to these records.

**Data sharing with the NINR/NIH:** As a condition of this National Institutes of Nursing Research (NINR) award, de-identified patient data will be shared by the researchers with the NINR and stored electronically on an NIH password protected secure server (<https://cdrns.nih.gov/>). The purpose of sharing this information is to build a NINR repository of data using Common Data Elements (CDE) for future research purposes among the general scientific community and for public health benefit. Patients will be allocated a random identifier through the NIH supported GUID Tool. The GUID Tool (<https://cdrns.nih.gov/node/39>) is a customized software application that generates a Global Unique Identifier for each study participant. The GUID is a subject ID that allows researchers to share data specific to a study participant without exposing personally identifiable information (PII). The GUID is made up of random alpha-numeric characters and is NOT generated from PII/PHI. As such, it has been approved by the NIH Office of General Counsel. GUID Generation complies with HIPPA regulations for the protection of PII/PHI. Patients are made aware of this data sharing agreement with the NINR/NIH in the study's Informed Consent document. Further protections are afforded to participants through an NIH Certificate of Confidentiality conferred upon the study.

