### 3.0 Intervention to be studied

**RESP-FIT.** The RESP-FIT program is a 6-week respiratory muscle strength training intervention adapted from previous RMST training regimens (Sapienza, Troche, Pitts & Davenport, 2011; Martin & Davenport, 2011; Hegland et al., 2016), consisting of 1) five training days/week using a combined IMST/EMST training device to which we will add Bluetooth enabled frequency and pressure intensity feedback monitoring to determine adherence and precise timing for device threshold intensification (i.e., increasing resistance training) 2) individualized, progress-based text message training reminders and prompts related to timing and intensification calibration, and 3) use of a Fitbit for remote monitoring of physical activity and hours slept at night. The training device is calibrated at 70% of each individual’s baseline PImax and PEmax. Similar to other muscle strength training programs, exercises are done at regular intervals during the week (5 breaths, 5 times a day, 5 days a week; the participant will receive graphical illustration of RESP-FIT training frequency and intensity achieved, and based on their training regimen, will be prompted and/or reinforced via SMS text messaging. Note, this feedback system allows personalized, calibrated, and efficiently timed adjustments of resistance training intensity as respiratory muscle strength improves, rather than simply increasing levels weekly. As the use of an accelerometer or remote tracking device alone may affect physical activity, a control group will receive only the Fitbit. **This study proposes to assess the initial efficacy of RMST by obtaining estimates of variability in fatigue secondary to dyspnea, using a technologically-enhanced RESP-FIT intervention.**

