**Randomization and Training Regimen:** Following collection of pre-training baseline measures, participants will be randomly assigned 50/50 to either a Standard of Care (SOC) Control Group (n=15), or a SOC + EMST/IMST Group (n=15). Participant randomization will be stratified by gender and dyspnea grade as measured on the MMRC. Those participants assigned to the SOC control group will receive a Fitbit monitoring device, but no intervention beyond that which is typically provided to patients seen within the MUSC Clinic. Participants randomly assigned to receive SOC+EMST/IMST will receive six weeks of clinician-guided, scripted RMST. This training will be facilitated by the PI using a custom-designed and constructed EMST/IMST trainer. Non-invasive measurement of maximum expiratory and inspiratory pressures (PEmax and PImax; described previously) will be obtained in order to set pressure threshold of the EMST/RMST device. The first week of EMST/IMST training will be conducted with the device set at 75% of the average initial PEmax collected at pre-training baseline. After a nose clip is placed the participants will be taught a four-step procedure: 1) take a breath in, 2) wrap lips tightly around the EMST/IMST trainer mouthpiece, and 3) exhale quickly and forcefully until you hear the popping or whistling sound of the device valve opening, and 4) continue blowing forcefully for two seconds. Once the participant is able to do a five-breath trial, another five-breath trial will be completed with the participant allowed as much independence as appropriate. The participant will receive a text message each day reminding them to complete his or her training and "remain active today." Participants in the SOC group will receive a text message reminding them to "remain active today." The daily training session will be as follows: 1) five sets of five-breath exhalations (25 breaths total) completed each training day, 2) each exhalation within a set will be separated by approximately one minute, and 3) each five-breath training set will be separated by five minutes. A Bluetooth-enabled "use" button on the EMST/IMST device will log the times the participant has used their training device. Each participant will be provided with a diary to record five sets of five-breath training trials on five days each week. Our experience indicates that EMST/IMST takes approximately 20 minutes each day. PEmax will be reassessed weekly, by the research clinician across the six-week treatment period and readjusted to 75% of the participant's current PEmax. If no changes in PEmax are observed week to week, treatment

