## 18.0 Drugs or Devices

This study does not involve the use or storage of any drug product. All investigational supplies and materials are readily commercially available and are not industry regulated. All study supplies (breathing inhalers and tablets) will be inventoried and stored in a locked cabinet, behind a locked door by the researchers. Study supplies will be dispensed individually to each participants after enrollment and group assignment.

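### The plan analyses change in steps and active time, but no procedure it describes yields a Fitbit baseline before training starts

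*Combined protocol and SAP*

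**What the plan says.** **Analysis.** Section 12.0 (Statistical Analysis) describes a plan "with a secondary focus on changes observed on fatigue and dyspnea scales", and the same list goes on to "physical activity (steps per day and active hours per day". It adds: "Pre- and post-intervention data will be analyzed for correlation between symptom severity and respiratory muscle strength (PImax and PEmax) along with mean steps per day". Exploratory Aim 4 in section 1.0 asks whether better symptoms lead to more physical activity and better sleep on the tracker. Section 10.0 also files activity under that exploratory aim.

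**Promised time points.** The opening of section 10.0 says the tabulated data are collected at baseline, 6 weeks and 14 weeks. The paragraph just before Monitoring period says every dependent variable is obtained at baseline, 3 weeks, 6 weeks and 14 weeks.

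**Procedure.** Section 10.0 (Randomization and Training Regimen) gives the order: "Following collection of pre-training baseline measures, participants will be randomly assigned 50/50", and then "Those participants assigned to the SOC control group will receive a Fitbit monitoring device". Section 18.0 says "Study supplies will be dispensed individually to each participants after enrollment and group assignment". The Objective Measures table names baseline for the pressure measurements and lung function, but gives steps, active minutes and sleep only a daily time point. The Activity Tracking paragraph says each participant gets a tracker and does not say when.

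**Tracker effect.** Section 3.0 justifies the Fitbit-only control group with the words "As the use of an accelerometer or remote tracking device alone may affect physical activity".

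**The concern.** Lung function, respiratory pressures and questionnaires can be recorded at one visit before randomisation. Mean daily steps cannot, because they need several days of wear. If the tracker is first worn after allocation, the earliest step counts come from people who may already be training and who are receiving daily texts telling them to stay active. The baseline that the change and pre/post analyses need would then not exist, and it cannot be recovered later.

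This matters even in a pilot that disclaims hypothesis testing. Section 12.0 (Sample Size) says the study is meant to supply estimates of variability for the secondary measures, and section 1.0 looks ahead to a large efficacy trial. Without a baseline, the trial cannot estimate the standard deviation of change in steps or the pre-post correlation, which are planning inputs for that next trial.

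**Working it through.** **1. The passages side by side.**

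| Question | What the protocol gives |
|---|---|
| Is a Fitbit baseline needed? | Yes, for change in steps and active hours and for pre-intervention mean steps (12.0) |
| Is one promised? | Yes, in two blanket statements covering all measures (10.0) |
| Is wear before training scheduled? | No run-in or wear window appears anywhere |
| When do controls get the tracker? | Described after assignment (10.0) |
| When does the training arm get it? | Not stated; section 18.0 suggests after assignment, but its list of supplies does not name the Fitbit |
| Is a baseline window defined for steps? | No, only a daily time point |

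Section 12.0 also lists the post-intervention data to be compared with baseline: PEmax, PImax, PROMIS and SGRQ. Fitbit data are absent from that list.

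**2. The plan's own precision figure.** Section 12.0 gives 95% half-widths of ±0.20 to ±0.78 for change-score standard deviations of 0.5 to 2.0. The formula is 1.96 × SD / √n. With the 25 expected completers, 1.96 × 0.5 / 5 = 0.196 and 1.96 × 2.0 / 5 = 0.784, so the figure reproduces. It covers self-efficacy, fatigue and dyspnea. No precision is stated for steps or active time.

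**3. Week 1 as a stand-in.** Suppose a share f of the effect is already present in week 1. Change measured from week 1 then keeps only (1 − f) of the effect: 75% at f = 0.25 and 50% at f = 0.5. The documents give no value for f, so these are illustrations.

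**4. What baseline adjustment would add (illustration).** Assume equal variances, and a correlation r between baseline and week-6 activity of 0.5 to 0.8. The documents give no value for r. Adjustment multiplies the variance of the between-arm comparison by 1 − r².

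- r = 0.5: 1 − 0.25 = 0.75; √0.75 = 0.87; standard error about 13% lower.
- r = 0.8: 1 − 0.64 = 0.36; √0.36 = 0.60; standard error 40% lower.

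With 25 completers, or 12 to 13 per arm, the unadjusted 95% half-width is 1.96 × √(2/n): 0.80 SD at n = 12 and 0.77 SD at n = 13. Adjusted, it is 0.67 to 0.69 SD at r = 0.5 and 0.46 to 0.48 SD at r = 0.8.

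A simple change score multiplies the variance by 2(1 − r) instead. That is 1.0 at r = 0.5, so no gain, and 0.4 at r = 0.8.

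**The case against.** **The protocol does promise a baseline.** Section 10.0 says so twice, so a reader should not conclude that none was intended. This stands as a point about intent. It does not supply a procedure, because a blanket statement cannot produce a multi-day step count from a tracker not yet worn.

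**The timing of issue is partly inferred.** A reader might infer that the protocol expressly gives the Fitbit to both arms after allocation. It does not. The sentence in section 10.0 concerns controls and mainly describes what they receive. Section 18.0 defines its supplies in the words "All study supplies (breathing inhalers and tablets) will be inventoried and stored in a locked cabinet", which leaves out the Fitbit. This stands. The gap rests on the absence of any scheduled wear before training, and the issue wording only supports it.

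**The outcome may be only exploratory.** Sections 1.0 and 10.0 say so. The list in section 12.0 ends with sex-based differences, so the word changes need not govern every item. This stands and lowers the weight of the point. Even so, the sentence on pre- and post-intervention data names mean steps separately.

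**The control group already handles tracker reactivity.** This is correct. A reader might infer that the activity comparison is biased, but randomisation protects a comparison of later activity. The loss is in change, in planning estimates and in precision.

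**The precision gain belongs to an analysis the plan does not specify.** This is also correct, and the correlation is assumed. The gain is therefore an illustration and should not be turned into an equivalent number of participants.

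**Conclusion.** The point holds as a gap between what is promised and what is done. Sections 10.0 and 12.0 assume pre-intervention Fitbit values, and no described procedure can produce them. Within-participant change in steps and active time, its standard deviation, the correlation with pre-intervention steps and any baseline adjustment are all unavailable as the plan is written. The between-arm comparison of later activity remains valid.

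The conclusion rests on reading the protocol as complete about tracker wear. If the site in fact issues trackers at consent and waits before training, the remedy is only to write that down. The 13% to 40% reduction in standard error depends on the assumed correlation of 0.5 to 0.8 and on using an adjusted analysis. Because this is a feasibility pilot and activity is mainly exploratory, this is a worthwhile and cheap improvement, not a flaw in the trial's main purpose.

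**What to change.** 1. Issue the Fitbit to every participant at Visit 1, after consent.
2. Collect about 7 days of wear before training and the activity texts start. Where this can be done without another on-site visit, collect it before the allocation is revealed as well.
3. Define baseline as mean daily steps and mean daily active minutes over valid days in that window, and state what makes a day valid.
4. Compare week-6 activity between arms, adjusted for that baseline.
5. Reconcile the Objective Measures table, the randomisation paragraph and the all-variables statement in section 10.0 with section 18.0, and give activity one outcome tier throughout.

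If the wear window is not feasible, remove the change-from-baseline analyses of Fitbit outcomes and report only the between-arm comparison.

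**Cost.** About one week's delay per participant, and possibly one extra contact. Participant Compensation in section 10.0 pays 25 dollars for screening and 25 dollars for enrolment but totals them as 50 dollars at Visit 1, which suggests that the two share a visit. Some tracker reactivity will remain in the baseline week. It is common to both arms, so it should not distort the between-arm comparison, but it may blur within-participant change.

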#### **14.0 Withdrawal of Subjects**

Participants may voluntarily elect to withdraw their consent at any time for any or no given reason while enrolled in the study. The PI may withdraw participants from the study at any time if they decide it is in the participant's best interest, if they do not follow the investigator's instructions, and/or if they fail to maintain contact with the researchers or attend study visits. Withdrawals of participants may also occur if there is a protocol violation or early study closure. All data gathered from withdrawn participants will be used in the analysis plan under an Intention-to-Treat (ITT) model.

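### The stated within-group precision fits 25 participants, more than either arm of 15 can supply, and no between-arm estimate is specified for the continuous Aim 2 outcomes

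*Combined protocol and SAP*

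**What the plan says.** Section 10.0 (Randomization and Training Regimen) assigns participants 1:1 to standard of care (n=15) or standard of care plus training (n=15), stratified by gender and MMRC grade. It has all dependent variables measured in all participants.

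The Sample Size paragraph of section 12.0 recruits about 30 in total and states "we anticipate that approximately 25 of these patients will complete all study-related visits". For self-efficacy, fatigue and dyspnea it then says "we use an in intent-to-treat analyses and 95% confidence interval (CI) estimates of the within group change scores (pre- to post-treatment", with half-widths of ±0.20 to ±0.78. It adds: "These correspond to estimated standard deviations of change scores of these variables, ranging from 0.5 to 2.0". The same paragraph limits its ambition: "The purpose of this pilot study is not to confirm or refute hypotheses about treatment effectiveness"; the study seeks instead to show feasibility and "to obtain estimates of variability for the secondary outcome measures". Section 14.0 adds: "All data gathered from withdrawn participants will be used in the analysis plan under an Intention-to-Treat (ITT) model".

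On estimators for the continuous outcomes:
- The opening of section 10.0 refers to a within-participant effect size.
- The Statistical Analysis paragraph of section 12.0 says "Post-Intervention data collection will include PEmax, PImax, PROMIS and SGRQ scales (see above) to compare to baseline measures". It also mentions correlations between symptoms and muscle strength, and sex differences.
- Two-sample tests for continuous data appear once: "T-tests or non-parametric Wilcoxon rank sum tests will be used to compare continuous demographic and baseline clinical variables". Chi-square and Fisher tests are for categorical data.

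**The concern.** There are two linked problems. First, a precision labelled as within-group should rest on the size of a group, and the printed figures look too narrow for arms of 15.

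Second, the trial randomises, yet no listed estimator for the continuous Aim 2 outcomes sets one arm against the other. Change within an arm cannot separate training from influences that both arms share. Section 3.0 names one such influence itself: it includes a control group because wearing a tracker may alter physical activity. Both arms also receive a daily text about staying active.

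At stake are the preliminary efficacy evidence sought in Aim 2 and the variability estimates intended to inform the large efficacy trial that section 1.0 names as the next phase.

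**Working it through.** **Inputs.** From section 12.0 (Sample Size): 95% confidence, taken as two-sided; SD of change 0.5 to 2.0; half-widths ±0.20 to ±0.78; about 30 recruited and about 25 completing, both arms together. From section 10.0: 15 per arm. The n behind the precision is not stated.

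**Step 1: reproduce the stated figure.** The half-width for a mean change is 1.96 × SD / √n.
- n = 25: 1.96 × 0.5 / 5 = 0.196 (0.20) and 1.96 × 2.0 / 5 = 0.784 (0.78). Both ends match.
- n = 24 gives 0.200 and 0.800; n = 26 gives 0.192 and 0.769. Neither matches both ends.
- Allowing for rounding, 0.20 at SD 0.5 needs n between (0.98/0.205)² = 22.9 and (0.98/0.195)² = 25.3. For 0.78 at SD 2.0, n must lie between (3.92/0.785)² = 24.9 and (3.92/0.775)² = 25.6. Only n = 25 meets both conditions.
- With Student t, no n gives both ends: n = 25 gives 0.206 and 0.826, and n = 28 gives 0.194 and 0.776.

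So the figure uses the expected completers of both arms together. All 30 pooled would give ±0.18 to ±0.72 (z), so it is not the full randomised set either.

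**Step 2: recompute for one arm.** The z half-width is 1.96 × SD / √n. The t half-width replaces 1.96 by 2.145 (14 df), 2.179 (12 df) or 2.201 (11 df).

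| n in the arm | z, SD 0.5 to 2.0 | t, SD 0.5 to 2.0 | Ratio to the n = 25 z figure: z | Ratio: t |
|---|---|---|---|---|
| 15 (no dropout) | ±0.25 to ±1.01 | ±0.28 to ±1.11 | √(25/15) = 1.29 | 1.41 |
| 13 | ±0.27 to ±1.09 | ±0.30 to ±1.21 | √(25/13) = 1.39 | 1.54 |
| 12 | ±0.28 to ±1.13 | ±0.32 to ±1.27 | √(25/12) = 1.44 | 1.62 |

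The z ratios isolate the error in n. The t ratios add the move from z to t. The rows for 12 and 13 assume near-equal dropout. With a 10 v 15 split of completers, the smaller arm would have ±0.36 to ±1.43 (t).

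**Step 3: precision of a between-arm difference in change, for reference.** The half-width is t × SD × √(1/n₁ + 1/n₂), assuming the same SD in both arms.
- 15 v 15 (28 df, t = 2.048): 2.048 × 0.3651 × SD = ±0.37 to ±1.50.
- 12 v 13 (23 df, t = 2.069): 2.069 × 0.4003 × SD = ±0.41 to ±1.66.

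This is a different quantity from the one whose precision section 12.0 states, and the plan makes no claim about it.

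**Step 4: look for an arm contrast.** Taking the listed analyses in turn: the within-participant effect size and the comparison with baseline are within-person; the confidence intervals are for within-group change; the t and rank sum tests are confined to demographic and baseline variables; chi-square and Fisher tests are for categorical data; the correlations and sex differences do not compare arms. None is a between-arm estimate of a continuous Aim 2 outcome.

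**The case against.** The strongest reply is that this is a pilot. Its size was set on pragmatic grounds, effectiveness testing is disclaimed, and the outcomes are secondary. That stands as far as power goes: the printed precision did not determine the sample size, so a reader should not infer that 30 is the wrong number. It does not excuse a per-group precision that no group can deliver, nor does it remove Aim 2.

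It can also be said that a control-group design, with a stated reason for the control arm, implies a comparison. That is fair. The plan is under-specified, and nothing in it rules a comparison out.

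Three stronger readings are tempting, and the documents do not support them:
- **That the analysis will pool the arms.** The plan does not say so. The total may simply have been put into a per-group formula.
- **That the information needed for the next trial will be lost.** The team will hold the raw data, and section 12.0 sends de-identified patient data to a repository. Even per-arm summaries would go far: with complete pairs, the pre, post and change SDs give the covariance as (SDpre² + SDpost² − SDchange²)/2. From this, the common-slope baseline-adjusted difference and its residual SD follow.
- **That the error in n makes the interval about 1.6 times as wide.** That figure mixes in the switch from z to t.

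**Conclusion.** The point holds. The stated ±0.20 to ±0.78 is wrong as a per-arm precision, even with no dropout. The error in n alone makes the interval 1.29 times as wide with all 15, and 1.39 to 1.44 times with 12-13 completers. Using t, as is usual at this size, raises these to 1.41 and 1.54 to 1.62. If pooling was intended, the resulting change mixes trained and untrained participants and describes neither arm, so the text needs correcting on either reading.

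No between-arm estimate is specified for the continuous Aim 2 outcomes. The gap is a planned estimate that uses the randomisation.

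The conclusion rests on n = 25 being inferred (though it is the only fit), on near-equal dropout for the 12-13 figures, and on a common SD for the between-arm figures. The SDs are the plan's own and come without scale or source. The consequence is modest, and worth fixing because the fix is cheap.

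**What to change.** 1. **Sample Size paragraph, section 12.0.** Restate the within-group precision per arm, giving both ±0.28 to ±1.11 (t, n = 15) and ±0.30-0.32 to ±1.21-1.27 (t, 12-13 completers). Say which n is used, because the analysis is called intent-to-treat while the present figure is for completers.
2. **Statistical Analysis and Sample Size paragraphs.** For each continuous secondary outcome, add the between-arm difference at week 6, as randomised, adjusted for its baseline value, with a 95% CI. Present it as estimation and not as a test. Keep the within-arm changes as descriptive. Adjusting for the stratification factors is optional at this size. The unadjusted half-widths in step 3 of the working can be quoted as a guide.
3. **What the contrast estimates.** The opening of section 10.0 has all 30 participants, 15 per group, using SAMS. Section 3.0 gives controls only the Fitbit, and the randomisation paragraph gives them the Fitbit with no intervention beyond usual care, plus the activity text. These passages must be reconciled so that it is clear whether SAMS is shared by both arms or is part of the difference.

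The cost is wording, a wider stated interval and slightly more analysis work. No new patients or visits are needed. The week-6 data are already planned if the schedule in section 10.0 holds. One entry needs aligning with it: the Participative Measures table lists the PROMIS dyspnea functional limitations scale at baseline only.
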